9.4 DATA SOURCES

We will utilize medical and pharmacy claim records from [REDACTED] medical and pharmacy claims data. This database is comprised of adjudicated claims for more than 150 million commercially insured and Medicare lives in the US. Data between 2014 and 2020 will be extracted, with the first patient follow-up period for tiotropium 1.25 mcg dose patients starting in October of 2015. This longitudinal database allows documentation and analysis of the patient journey from diagnosis to intervention and follow-up. The database includes patients in the majority of three-digit zip codes and in every metropolitan statistical area of the US. It also covers data from 90% of US hospitals, 80% of all US doctors, and represents 85% of the Fortune 100 companies, with current HIPAA (Health Insurance Portability and Accountability Act) regulations. The database is constructed from a variety of geographic regions and employer groups and maintains a level of diversity while representing the overall trend in commercial health plan coverage. The underrepresentation of the population aged 65 years and older may affect external validity in the case of Medicare, Medicare Advantage or Medicaid patients.

Proprietary confidential information © 2021 Boehringer Ingelheim International GmbH or one or more of its affiliated companies

9.5 STUDY SIZE

There are 25,291 patients with a prescription claim for tiotropium (1.25mcg, October 2015-May 2020) identified for analysis and 1,125,657 patients with ICS/LABA prescription claims (July 2014-May 2020). After excluding patients with COPD there are 17,882 patients in the Tio group and 921,804 patients in the ICS/LABA group. Further inclusion-exclusion criteria as well as restricting the Tio group to those with concurrent ICS monotherapy, will be applied to arrive at the final sample.

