9. RESEARCH METHODS

9.1 STUDY DESIGN

1. Patients with least two asthma diagnosis (ICD 9 CM: 493.xx or ICD 10: J45-J45.999) will be included.
2. Patients will be required to be concurrently on ICS+Tiotropium (specifically Tiotropium Respimat® 1.25 mcg) or ICS/LABA.
3. Patients with least two diagnosis of COPD at any time during the study period will be excluded.
4. Patients less than 12 years of age will be excluded.
5. Patients will be required to have enrollment for at least 6 months prior to ICS+Tio or ICS/LABA use.
6. Patients on biologics within 6 months prior to ICS+Tio or ICS/LABA use will be excluded.
7. Patients with prior Tio or ICS/LABA use during the 6-month baseline period will be excluded.
8. Patients with urinary bladder obstruction, urinary retention, and glaucoma will be excluded.
9. After the PSM process, unmatched patients will be excluded.

Patients will be classified into two groups based on the exposure on the index date: 1. ICS+Tio; and 2: ICS/LABA. The date of concurrent medication initiation will be defined as the index date based on the date of the first prescription claim defining their add-on medication. We will record various baseline measures, including demographics such as gender, age, and region, comorbidity level defined using Charlson Comorbidity Index (CCI), other specific comorbidities not included in the CCI ([Table 1](#)), inhaled medication use, and control level as defined in Table 1. Additionally, we will classify patients based on their daily ICS dose levels as 'low dose ICS', 'medium dose ICS', and 'high dose ICS'. The dose levels will be assigned per GINA 2020 criteria (Global Initiative for Asthma. Global Strategy for Asthma Management and Prevention 2020). Medications that are available with only two dose level indications will be tagged as 'low' for the lower of the two dose levels, and 'high' for the highest dose level.

Proprietary confidential information © 2021 Boehringer Ingelheim International GmbH or one or more of its affiliated companies

Table 1: Baseline Parameters and Variable Definitions

Variable Name and Type	Description and Definition	Covariate Adjustment Method
Demographics	Age (5-year increments), Gender,	PSM
Region	Region (Northeast, Midwest, South, West)	PSM
CCI	Charlson Comorbidity Index score	PSM
Inhaled medication use	Identified using unique claims during the baseline period	PSM

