Control Status: Not Well Controlled or Well Control	
“Not Well Controlled” if patient has any one of the following events
 
 • Prescription for OCS • Asthma-related ER • Asthma-related hospitalizations 
“Well controlled” if patient has none of the above events
 
(Ref: Stempel JACI 2005)
	PSM
ICS history	Defined by use of ICS monotherapy prior to index date	PSM
ICS history duration	Days on ICS monotherapy prior to index date	PSM
ICS dose level	Daily dose of ICS classified as low dose ICS, medium dose ICS, and high dose ICS	PSM
Season	Season of cohort entry (Summer, Spring, Fall, Winter)	PSM
Index year	Year of the index date	PSM
All-cause resource use	All-cause hospitalizations, ER visits, outpatient visits	PSM
Other asthma medications	Leukotriene modifiers	PSM
Medication history	Polypharmacy calculated based on number of unique medications	PSM
Insurance type	Identified using payer type data field	PSM
Hypertension	Identified using appropriate ICD codes. Coded as binary (yes/no) variables	PSM
Allergic rhinitis	Identified using appropriate ICD codes. Coded as binary (yes/no) variables	PSM
Sinusitis	Identified using appropriate ICD codes. Coded as binary (yes/no) variables	PSM
Obstructive sleep apnea	Identified using appropriate ICD codes. Coded as binary (yes/no) variables	PSM
Gastro-esophageal reflux disease	Identified using appropriate ICD codes. Coded as binary (yes/no) variables	PSM
Obesity	Identified using appropriate ICD codes. Coded as binary (yes/no) variables	PSM
Cardiovascular disease	Identified using appropriate ICD codes. Coded as binary (yes/no) variables	PSM
Diabetes	Identified using appropriate ICD codes. Coded as binary (yes/no) variables	PSM

Proprietary confidential information © 2021 Boehringer Ingelheim International GmbH or one or more of its affiliated companies

Table 1: Baseline Parameters and Variable Definitions (cont)

Variable Name and Type	Description and Definition	Covariate Adjustment Method
Renal failure	Identified using appropriate ICD codes. Coded as binary (yes/no) variables	PSM
Arthritis	Identified using appropriate ICD codes. Coded as binary (yes/no) variables	PSM
Depression	Identified using appropriate ICD codes. Coded as binary (yes/no) variables	PSM
Osteoporosis	Identified using appropriate ICD codes. Coded as binary (yes/no) variables	PSM
Cancer (excluding basal cell carcinoma)	Identified using appropriate ICD codes. Coded as binary (yes/no) variables	PSM

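### The ICS/LABA claims window opens before the tiotropium 1.25 mcg window, no criterion sets a common index-date start, and year and season in the score only partly make up for it

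*Combined protocol and SAP*

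**What the plan says.** Section 9.5 gives the two source counts over different periods: "25,291 patients with a prescription claim for tiotropium (1.25mcg, October 2015-May 2020") and "1,125,657 patients with ICS/LABA prescription claims (July 2014-May 2020"). Section 9.4 confirms the later tiotropium start: "with the first patient follow-up period for tiotropium 1.25 mcg dose patients starting in October of 2015". The same section sets the extraction period: "Data between 2014 and 2020 will be extracted".

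Section 9.1 defines the tiotropium group by one product, "specifically Tiotropium Respimat® 1.25 mcg". It asks for a six-month baseline ("Patients will be required to have enrollment for at least 6 months prior to ICS+Tio or ICS/LABA use") and sets the index date from the add-on claim ("The date of concurrent medication initiation will be defined as the index date based on the date of the first prescription claim"). None of its nine criteria sets a calendar start common to both groups.

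Calendar time is handled through the propensity score. Table 1 lists index year, defined as "Year of the index date", and on a separate row the season of cohort entry in four categories. Section 9.3.3 repeats both. Matching is 1:2 nearest neighbor, with no caliper and no exact-match variable stated. Balance is judged by p<0.05 and by SMD below 0.1. Interaction terms are one of the options if differences remain after matching.

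**The concern.** Section 9.1 describes a new-user comparison, which is cleanest when both groups start treatment in the same calendar period. Here an ICS/LABA patient can be indexed in early 2015, when no patient can yet be indexed on tiotropium 1.25 mcg. Whole-year index year cannot tell such a patient from one indexed in November 2015. Season helps, but it is a separate term and the scalar score can trade it off against other covariates.

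At stake is concurrency for the earliest tiotropium patients: if coding, care or exacerbation rates drifted during 2015, their comparators would carry that drift. The unmatched baseline tables promised in section 9.7.1 would also describe different calendar periods in the two groups.

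**Working it through.** The plan states no figure to reproduce; section 9.5 gives feasibility counts only.

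**1. Window lengths** (inclusive months, from section 9.5)
- ICS/LABA, July 2014-May 2020: (2020 − 2014)×12 + 5 − 7 + 1 = 71.
- Tiotropium 1.25 mcg, October 2015-May 2020: (2020 − 2015)×12 + 5 − 10 + 1 = 56.
- Difference: 71 − 56 = 15 months, of which 6 fall in 2014 and 9 in January-September 2015.

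July 2014 is printed as a claims window. Reading it as the first index month fits extraction from January 2014 plus six months of baseline. If July 2014 were instead the start of the data, entry would begin in January 2015 and the gap would be 9 months. The January-September 2015 months are in question either way.

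**2. Share of matched comparators from January-September 2015.** Assumed: flat monthly ICS/LABA entry, and tiotropium entry either flat or rising linearly from October 2015.
- Share of tiotropium patients indexed in 2015. Flat: 3/56 = 5.36%. Rising: (1+2+3)/(56×57/2) = 6/1596 = 0.38%.
- Matching on year only: 9/12 = 75% of the 2015 comparators precede October. Flat: 5.36% × 0.75 = 4.0%. Rising: 0.38% × 0.75 = 0.3%.
- Matching exactly within year and season, the best that these two covariates can do (taking December-February as winter and September-November as fall): one of three 2015 fall months and two of three 2015 winter months precede October. Flat: (2×1/3 + 1×2/3)/3 = 4/9, and 5.36% × 4/9 = 2.4%. Rising: (3×1/3 + 3×2/3)/6 = 1/2, and 0.38% × 1/2 = 0.2%.

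Season therefore narrows the gap without closing it: January, February and September 2015 remain even under exact year-by-season matching.

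**3. Simulated matching on the score.** Assumed: 3,000 tiotropium patients and 153,000 comparators, season in the score, greedy 1:2 matching, no caliper, one run per pattern. Share of all matched comparators indexed before October 2015:

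| Tiotropium uptake | Year categorical | Year linear |
|---|---|---|
| Rising | 0.2% | 2.0% |
| Flat | 4.0% | 10.6% |
| Front-loaded | 13% | 21% |

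The linear-year figures include 0.3% to 9.5% from 2014. Within the matched 2015 comparators alone, 68% to 83% preceded October. Another set of three runs with gradual uptake gave 0.5% to 1.0% overall. The plan does not say how year is coded.

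**4. Would the balance check see it?** Year and season are each compared as margins. Both margins can agree while the months within 2015 do not. In a further simulated match (year categorical, one additional covariate in the score), every year and season SMD stayed below 0.1 under flat, rising and front-loaded uptake, although most of the matched 2015 comparators preceded October. The post-matching remedies in section 9.1 depend on a detected difference, so they would not be triggered.

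**5. Pool left after a common start** (flat entry assumed, counts after COPD exclusion from section 9.5)
- Dropped: 921,804 × 15/71 ≈ 194,700.
- Remaining: about 727,000, and 727,000/17,882 ≈ 41 per tiotropium patient, against 921,804/17,882 ≈ 51.5 now.

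**The case against.** The plan does not ignore calendar time: year and season are both in the score, and season pulls matches for October-December 2015 patients towards fall and winter. That stands, and it is why the remaining share is small under flat or rising uptake.

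A reader might infer a positivity violation, because early comparators could not have received tiotropium 1.25 mcg. The design does not support that charge. Two comparators are matched to each tiotropium patient and unmatched patients are dropped, so the comparison concerns tiotropium-type patients. It needs a suitable comparator for each of them, not tiotropium eligibility for everyone in the pool.

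A reader might also treat all 15 of the 71 months as contaminated, or see a failure of the score model because 2014 has no tiotropium patients. If year is categorical, that absence drives the 2014 scores towards zero, so those patients are rarely chosen; any separation is mainly a fitting nuisance. The dispute is chiefly about the nine months of 2015. Only if year is linear do 2014 comparators enter in visible numbers.

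The effect on the result may also be negligible. If the affected comparators had a 20% different hazard (assumed), the comparator rate would move by roughly 0.04 × 0.20 = 0.8% at a 4% share, or 0.2% at a 1% share. No mechanism for a difference between early and late 2015 is documented. This limits the point to a minor one, but gives no reason to keep the unmatched windows.

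**Conclusion.** The point holds as a minor design improvement. The printed windows differ, no criterion aligns them, and separate year and season terms leave room for non-concurrent comparators that the planned balance checks would miss. The affected share is about 0.2% to 4% of matched comparators under flat or rising tiotropium uptake with flat ICS/LABA entry. It could exceed that if uptake was front-loaded or year is linear. These ranges rest on assumed entry patterns, because the documents give no index dates by month. It would go too far to conclude that the primary hazard ratio is biased: no such bias has been shown, and the illustration above suggests a small effect at the shares thought likely.

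**What to change.** Add a selection criterion to section 9.1 restricting index dates in both groups to October 2015-May 2020, and restate the ICS/LABA count in section 9.5 and the abstract for that window. When doing so, reconcile the October 2015 start with the statements in the abstract and section 7 that date US availability of tiotropium to 2016.

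Optionally, match exactly on calendar quarter of the index date: 1 quarter in 2015, 16 in 2016-2019 and 2 in 2020 (the last incomplete), so 19 strata. Quarter entered only as another score term would still allow matches across quarters.

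The cost is one date filter and one recount. About 41 comparators per tiotropium patient would remain under flat entry, so 1:2 matching should stay feasible. That ratio precedes the new-user washout and the concurrent-ICS restriction, so confirm it in the attrition table.

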9.6 DATA MANAGEMENT

The data management plan is summarized below. Full details of the data management plan are documented in a separate NIS-Data Management and Review Plan (NIS-DMRP).

[figure not shown]
All established security and confidentiality procedures will be observed by BI and/or [REDACTED] personnel who are assigned appropriate access to the data. Enrolment data, medical claims, and prescription claims will be accessed from the administrative claims dataset. The analyses will be performed on limited data sets that are void of member protected health information and all results were shared in aggregate form only.

9.7 DATA ANALYSIS

9.7.1 Main analysis

Sample attrition at each step of the inclusion-exclusion criteria will be provided. We will develop the breakdown of the distribution of demographic, comorbidity, and baseline measures prior to and after the PSM (unmatched and matched cohorts). Significance of differences will be tested at $P<0.05$ for the matched cohort. Additionally, we will consider the use of standardized mean differences as noted above, in which $SMD <0.1$ indicates balance of baseline covariates. The primary endpoint measure is time to first severe exacerbation and severe exacerbation will be defined as a hospitalization or an ER visit with a primary diagnosis of asthma. We will calculate the time in days to first exacerbation. Also, as part of the primary end point analysis, we will develop KM curves based on initial exposure and conduct time varying Cox proportional hazards modeling accounting for changes in exposure status over the follow up time to estimate the risk of exacerbation between ICS+Tio vs. ICS/LABA. Secondary endpoints will include a number of measures. We will calculate the time in days to first moderate-or-severe exacerbation defined as use of systemic corticosteroid or a hospitalization or ER visit with a primary diagnosis of asthma. KM curves based on initial exposure and time varying Cox PH models will be conducted for this secondary end point as well. We will also calculate and compare the rate of exacerbation, proportion of patients with exacerbations after 6 months and one year among the sub-population of patients having at least 6 months and a year of follow-up, respectively. We will report rates in patient-years to account for variable follow-up time. We will also compare the mean monthly (to account for variable follow-up time) per patient HCRU (all-cause and asthma related hospitalizations, ER visits, and outpatient visits) during the follow-up period, between the two groups. Proportions of patients with and without rescue medication use will be compared between the two groups as well.

Proprietary confidential information © 2021 Boehringer Ingelheim International GmbH or one or more of its affiliated companies

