Data analysis	Sample attrition at each step of the inclusion-exclusion criteria will be provided. We will develop the breakdown of the distribution of demographic, comorbidity, and baseline measures prior to and after the PSM (unmatched and matched cohorts). Significance of differences will be tested at $P<0.05$ for the matched cohort. Additionally, we will consider the use of standardized mean differences as noted above, in which $SMD <0.1$ indicates balance. The primary endpoint measure is time to first severe exacerbation and severe exacerbation will be defined as a hospitalization or an ER visit with a primary diagnosis of asthma. We will calculate the time in days to first exacerbation. We will conduct Cox proportional hazards modeling to estimate the risk of exacerbation and provide corresponding KM curves for the primary endpoint. Exposure to each of the study comparators (ICS+Tio and ICS/LABA) will be recorded using time-varying covariates for all primary and secondary endpoints. ICS+Tio vs. ICS/LABA will be the key independent variable and medication exposure will be a covariate included in the regression. Secondary endpoints will include time (in days) to first moderate-or-severe exacerbation defined as use of systemic corticosteroid or a hospitalization or ER visit with a primary diagnosis of asthma. Cox PH and KM curves will be conducted for this secondary end point as well. We will also calculate and compare the rate of exacerbation, proportion of patients with exacerbations after 6 months and one year among the sub-population of patients having at least 6 months and a one year of follow-up, respectively. We will report rates in patient-years to account for variable follow-up time. We will also compare the mean monthly (to account for variable follow-up time) per patient HCRU (all-cause and asthma related hospitalizations, ER visits, and outpatient visits) during the follow-up period, between the two groups. Proportions of patients with and without rescue medication use will be compared between the two groups as well.
----------------------	--

Proprietary confidential information © 2021 Boehringer Ingelheim International GmbH or one or more of its affiliated companies

5 . AMENDMENTS AND UPDATES

None

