Pneumonia	Identified using appropriate ICD codes. Coded as binary (yes/no) variables	PSM
Acute bronchitis	Identified using appropriate ICD codes. Coded as binary (yes/no) variables	PSM
Dyspnea	Identified using appropriate ICD codes. Coded as binary (yes/no) variables	PSM
Alcohol dependence	Identified using appropriate ICD codes. Coded as binary (yes/no) variables	PSM
Smoking dependence	Identified using appropriate ICD codes. Coded as binary (yes/no) variables	PSM

Using propensity score matching (PSM) technique, we will develop matched cohorts of patients between the ICS+Tio and ICS/LABA groups. We will conduct 1:2 matching using nearest neighbor matching approach. Upon completion of matching, we will assess whether the cohorts are balanced by examining the statistically significant differences at $p < 0.05$. We will also assess balance by calculating standardized mean differences (SMD). An SMD < 0.1 will be considered balanced. Follow-up time will be calculated between index date and 'Censor date' which will be defined as the date of either one of the following events: 1. Date of first exacerbation, 2. Date of medication switch, 3. Discontinuation of medication (defined as date of prescription claim plus days' supply, plus 50% additional days), 4. Enrollment end date, or 5. Last date available in the dataset/End of study period. In this "new user", study design, primary analysis will be an "as-treated" analysis. In order to attribute events and outcomes to patients during the time that they are exposed to treatment (based on days-supply of prescription claims + a buffer window) as well as account for differences in inter-group adherence levels, we will use a time-varying covariate approach to classify drug exposure time for each comparator drug during follow up. This approach has been chosen to minimize bias based on potentially large differences in medication adherence rates, by only attributing outcomes to the time in which patients have medication in their possession based on days' supply as described below. For each individual study drug, we will identify and define medication exposure and non-exposure windows during the follow-up time for each medication using the date of prescription filled plus the days' supply listed on the prescription claim plus 50% additional days (to account for residual doses in canister, poor real-world adherence and latency of drug effects). For example, exposure start and stop dates

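### Follow-up ends at the first exacerbation, yet the 6-month and one-year exacerbation proportions are confined to patients with that much follow-up, so for the event that ends follow-up they are zero by construction

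*Combined protocol and SAP*

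**What the plan says.** Section 9.1 measures follow-up from the index date to a censor date, "defined as the date of either one of the following events: 1. Date of first exacerbation, 2. Date of medication switch", with discontinuation, end of enrolment and end of data as the remaining three. It does not say whether the exacerbation meant is severe (asthma-primary hospitalization or ER visit, section 9.3.2.1) or moderate-or-severe (which adds systemic corticosteroid use, section 9.3.2.2). No other follow-up window is defined for any endpoint.

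Section 9.7.1 computes the share who have "exacerbations after 6 months and one year among the sub-population of patients having at least 6 months and a year of follow-up". The Data analysis part of the Abstract has the same restriction: "sub-population of patients having at least 6 months and a one year of follow-up". Section 9.3.2.2 does not settle the matter, because it lists the proportion without a time horizon or severity.

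Two further statements bear on who reaches 6 or 12 months. Section 9.1 ends follow-up at "Discontinuation of medication (defined as date of prescription claim plus" the days' supply and a 50% extension. The same section plans to "identify and define medication exposure and non-exposure windows during the follow-up time", and section 9.7.1 describes the Cox model as "accounting for changes in exposure status over the follow up time".

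**The concern.** The denominator is selected on the outcome. If the event ends follow-up, having at least six months of follow-up means not having had the event in the first six months. A proportion meant to describe early exacerbations then excludes everyone who had one.

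At stake are secondary measures that readers will take as the 6- and 12-month risks in the matched cohort. The analyst would have to choose a workable reading after the data are in hand, and the possible readings give different populations and different numbers. A comparative protocol should settle that choice in advance.

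**Working it through.** The plan states no event rate, proportion or event count for these measures, so there is no figure of its own to reproduce.

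**Step 1: the zero, with no assumed rate.** Let T be the time to the exacerbation that ends follow-up, C the earliest of the other four end dates, and L the landmark (6 or 12 months). Taking the censor date as the earliest of the five, follow-up is F = min(T, C). If F ≥ L then T ≥ L, so P(T < L | F ≥ L) = 0 in both groups. The only exception is an event on the cut-off day itself.

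**Step 2: the readings side by side.**

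- *A moderate-or-severe event ends follow-up.* Both proportions by the landmark are zero.
- *Only a severe event ends follow-up.* The severe proportion is zero. Early moderate events can count, but every patient with an early severe event is dropped.
- *'After' means later than the landmark.* The measure covers only patients event-free to the landmark (for the event that ends follow-up) and runs to whenever each patient's follow-up stops. It has no fixed horizon and is not a 6- or 12-month risk.
- *Follow-up was meant to continue past an exacerbation.* The proportions would then be sensible, but no section defines such a follow-up.

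**Step 3: size under the first two readings (illustration).** Assume independent constant hazards, severe S = 0.05 and moderate M = 0.4 per year. Neither comes from the documents.

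- Severe proportion without truncation: 1 − exp(−S·L). At 0.5 year, 1 − exp(−0.025) = 2.5%; at 1 year, 1 − exp(−0.05) = 4.9%.
- Moderate-or-severe without truncation: 1 − exp(−(S+M)·L). At 0.5 year, 1 − exp(−0.225) = 20.1%; at 1 year, 1 − exp(−0.45) = 36.2%.
- Moderate-or-severe among patients with no severe event before L: 1 − exp(−M·L). At 0.5 year, 1 − exp(−0.2) = 18.1%; at 1 year, 1 − exp(−0.4) = 33.0%.

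| Proportion by landmark | Without truncation, 6 / 12 months | Moderate-or-severe ends follow-up | Only severe ends follow-up |
|---|---|---|---|
| Severe | 2.5% / 4.9% | 0 / 0 | 0 / 0 |
| Moderate-or-severe | 20.1% / 36.2% | 0 / 0 | 18.1% / 33.0% |

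Over S = 0.02 to 0.2 and M = 0.2 to 0.8 per year, the relative shortfall in the last column runs from 1.6% (S = 0.02, M = 0.8, 12 months: 55.1% against 56.0%) to 47.5% (S = 0.2, M = 0.2, 6 months: 9.5% against 18.1%). Under these assumptions the truncated proportion depends on M alone, so a difference between groups in severe events would not show in it.

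**Step 4: the primary endpoint.** There is one censor date. If a steroid-only event sets it, the primary severe analysis stops there. With the same S and M and no other censoring, the share of first-year first severe events still observed is

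[S/(S+M)]·[1 − exp(−(S+M))] / [1 − exp(−S)] = (0.05/0.45)(0.3624)/(0.0488) = 0.826,

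so about 17% go unobserved. If moderate and severe events are related within patients, that censoring is also informative.

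**The case against.** The best defence is that nobody would program it this way. The censor date is set out within the as-treated, time-to-event description. Section 9.7.1 also speaks of variable follow-up time, rates in patient-years and mean monthly "per patient HCRU (all-cause and asthma related hospitalizations, ER visits, and outpatient visits) during the follow-up period". Asthma-primary hospitalizations and ER visits would make little sense as monthly means if follow-up stopped at the first one. This suggests a follow-up that continues past an exacerbation for the descriptive measures, and an empty numerator would be noticed at once.

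That argument stands as a view of likely intent, and it is why this point does not predict that the study will report zeros. A reader might infer as much, but the documents support only that the written rule produces them. Intent does not repair the text: no section defines the other follow-up. The separate data management and review plan was not available; it is cited for data management and quality control, not for endpoint definitions.

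A reader might also infer that differential persistence biases the comparison by a known amount, since section 9.1 wants to "minimize bias based on potentially large differences in medication adherence rates". The protocol gives neither size nor direction for those differences, so no such bias can be sized. Nor can a later-event proportion be set against a 6-month risk to show bias, because the two cover different lengths of time.

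**Conclusion.** The point holds and should be fixed. As written, the 6- and 12-month proportions are zero by construction for whichever exacerbation ends follow-up. That follows from the definitions alone. The percentages for the severe-only reading are illustrations resting on assumed, independent, constant hazards.

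Two opposite inferences about the primary analysis should be avoided. One is that the landmark problem undermines it; it does not, because the primary Cox and Kaplan-Meier analyses have no minimum-follow-up restriction. The other is that the primary analysis is untouched altogether. It is cut short if a steroid-only event sets the single censor date (about 17% of first-year first severe events at the assumed hazards), and the text does not exclude that.

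The sentence in section 9.7.1 also names the rate of exacerbation. If the restriction is meant to cover the rate, a rate counted up to the landmark is zero for the same reason.

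**What to change.** 1. State that each time-to-event analysis ends only at its own endpoint: severe for the primary, moderate-or-severe for the secondary. Step 2 depends on this.
2. Replace the restricted proportions with one minus the Kaplan-Meier estimate at 6 and 12 months in the full matched cohort, for each definition, with confidence intervals and a between-group difference. State the assumption that censoring at switch and discontinuation is non-informative. If a sub-population is kept instead, define it by continuous enrolment and data availability, not ended by an exacerbation, and state whether events after discontinuation count.
3. Reconcile censoring at discontinuation in section 9.1 with the non-exposure windows planned there and the changes in exposure status modelled in section 9.7.1.

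The cost is protocol wording plus read-outs at two time points from curves already planned for both definitions, or one changed denominator definition. The downside is that the Kaplan-Meier version relies on non-informative censoring, which may fail if patients stop or switch because of poor control. A rate of total episodes is optional. If one is wanted, follow-up for it must not end at the first event, and it needs an episode-separation rule and a count model with a person-time offset.
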